### 9.3.3. Endpoints of Interest

The endpoints of interest captured in the semi-annual reports are the following safety events of interest.

For the interim feasibility analysis and final safety report (where also information on patients, co-variates and outcomes, from SRQ as well as from the linked Patient/Prescribed Drug and other registers will be included) of pre-specified safety outcomes, the following events of interest have been pre-specified.

1. Hospitalized infections overall.
2. Opportunistic infections.
3. Herpes zoster (hospitalized).

090177e199570500\Approved\Approved On: 13-Feb-2022 20:25 (GMT)

4. Hepatitis.
5. Fractures.
6. NMSC.
7. Malignancies (overall, excluding NMSC).
8. Lung Cancer.
9. Lymphoma (overall and independently by subtype, including non-Hodgkin lymphoma, Hodgkin lymphoma, and chronic lymphatic leukemia).
10. CV events, including deep vein thrombosis/pulmonary embolism (DVT/PE).
11. Major Adverse Cardiovascular Events (MACE).
12. Myocardial infarction (MI)
13. Gastrointestinal (GI) perforations.
14. Progressive multifocal leukoencephalopathy (PML).
15. Interstitial lung disease, pending feasibility.
16. All-cause Mortality.

Given the age-dependent rate events of interest, analysis will be conducted in elderly patents aged  $\geq 65$  years.

This list may be extended with a reasonable number of additional sub-diagnoses or new health related outcomes as agreed to by ARTIS researchers and Sponsor before the interim feasibility analysis and final safety report. These decisions will be made prior to initiation of analyses and documented in a statistical analysis plan (SAP) kept on file by the Sponsor.

In addition, the final safety reports will include the number of tofacitinib-exposed pregnancies.

#### **9.4. Data Sources**

##### **9.4.1. SRQ**

SRQ is the source of disease activity information, measured by C-reactive protein (CRP), erythrocyte sedimentation rate (ESR), health assessment questionnaire (HAQ), number of swollen and tender joints, and patient's global assessment of disease (on a visual analog scale(VAS)) and doctor's evaluation on a Likert type scale. In addition, disease activity scores -28 (DAS 28), the European League Against Rheumatism (EULAR) response criteria, and the American College of Rheumatology criterion of improvement (ACR) can be calculated. Reflecting the changes in treatment paradigm, Table 1 shows how the disease activity in RA at the time of first biologic start has decreased over time. Although the system

was originally developed for RA, clinical variables of importance for specific rheumatic diseases have been added incrementally.

**Table 1. Temporal Trends in Average Disease Severity Scores at First Biologics Initiation in Swedish Patients with RA.**

	DAS28	HAQ	VAS	SJC	TJC	ESR	CRP
1998	6.6	1.6	55.6	15.0	14.4	47.0	43.7
1999	6.0	1.6	64.0	11.8	10.5	45.0	45.6
2000	5.7	1.5	62.6	10.3	9.4	39.3	38.5
2001	5.6	1.4	60.9	10.2	9.4	37.9	35.8
2002	5.6	1.4	59.1	9.8	9.0	38.6	35.5
2003	5.5	1.3	57.8	9.5	8.7	36.1	31.9
2004	5.4	1.3	58.1	9.2	8.6	35.7	30.7
2005	5.3	1.2	55.5	8.6	8.4	32.9	25.0
2006	5.2	1.2	56.6	8.4	8.0	31.5	23.8
2007	5.1	1.2	56.2	8.1	7.6	31.2	23.0
2008	5.1	1.2	56.4	7.8	8.0	28.4	18.7
2009	5.0	1.1	54.9	7.5	7.8	28.3	20.7
2010	4.9	1.1	55.7	7.0	7.4	27.4	18.0
2011	4.8	1.1	54.7	6.8	7.2	26.9	18.1
2012	4.9	1.1	58.0	6.8	7.4	25.6	18.1
2013	4.9	1.0	56.0	6.6	7.4	25.7	16.8
2014	4.8	1.1	54.7	6.1	6.9	25.9	17.0
2015	4.5	1.0	53.8	5.4	6.4	23.7	15.6
2016	4.5	1.0	54.4	5.2	6.6	24.5	14.2

CRP = C-reactive protein, ESR = Erythrocyte sedimentation rate; HAQ = Health Assessment Questionnaire; SJC = Swollen joint count, TJC = tender joint count, VAS = Visual analog score.

#### 9.4.2. SRQ/ARTIS Linkage

Endpoint information also derives from the linkage of SRQ/ARTIS to nationwide Swedish health care registers. Compared to the ADR reports, the register linkage has many advantages in providing data on all comorbidities that have been diagnosed, unbiased by incomplete reporting from physicians or by subjective assessments on causality. Importantly, it also allows us to obtain data on comparator cohorts, so that any potential risk increases can be evaluated in light of risks among patients on other treatments, and the general Swedish population. The drawback is a lag time of between 1 and 2 years from when an event occurs until it can be analyzed and reported using the national health care registers. This delay is caused by the annual curation of the Patient and Cancer registers by the National Board of Health and Welfare (ie, data from each year is only made available after internal processing, usually 9 to 12 months later, and the processing of data requests.

090177e199570500\Approved\Approved On: 13-Feb-2022 20:25 (GMT)

#### **9.4.3. The Patient Register and the Prescribed Drug Register**

The Swedish Patient Register provides information on all hospitalized (inpatient treated) patients, and all visits to non-primary outpatient care (such as a visit to a rheumatologist). Diagnoses are assigned by the discharging physician, as well as date of discharge, discharging hospital and department. Diagnoses are coded according to the International Classification of Diseases (ICD), with version 8 used until 1986, version 9 1987 to 1996 and version 10 (ICD10) since 1997.

In addition to data on safety outcomes and baseline comorbidities or disease history, the patient register is the source of comparator cohorts defined by diagnosis, but untreated with biologic agents.

The Prescribed Drug Register provides all retrievals of prescribed drugs in Sweden from July 2005, and may be used to aid correct classification of patients by their history of retrieved DMARDs, or to define subcohorts based on switches in treatment.

#### **9.4.4. The Swedish Cancer Register**

The Swedish Cancer Register was established in 1958 and provides data on date of cancer (and some selected pre-cancers) onset, and type of cancer according to the ICD classification and morphology/histology. About 99% of cancers have been morphologically verified. Reporting of incident cancers (including invasive malignancies as well as cancer in situ) is mandatory and semi-automated, resulting in an estimated coverage greater than 95%.

#### **9.4.5. The Contagious Disease Register**

The Contagious Disease Register provides events reported according the Communicable Diseases Act and the Communicable Diseases Ordinance on diseases that have mandatory reporting Sweden. The notifiable diseases also fall into different categories: subject to mandatory contact tracing, dangerous to public health and dangerous to society.

#### **9.4.6. The Medical Birth Register**

The Medical Birth Register contains prospectively provides data from antenatal, obstetric, and neonatal records since 1973, and covers all live and still births (but not all miscarriages) in Sweden. Among the variables covered are maternal age, parity, smoking and family situation in early pregnancy, and the infant's birth weight and length, gestational age (primarily based on ultrasound dating), and Apgar score. Complications and mother's and infant's morbidities are coded according to the ICD, with version 8 used until 1986, version 9 1987 to 1996 and ICD10 since 1997.

#### **9.4.7. The Cause of Death Register**

The Cause of Death Register is a national register containing information on date and cause of death (underlying and contributory) for all deceased residents, including deaths among Swedish residents who died abroad. Although the register was started in 1952, the data is considered complete since 1961.

#### 9.4.8. The Total Population Register

The Total Population Register lists data on residency at a given point in time since it was founded in 1961, and dates of emigration/immigration for all subjects ever resident in Sweden since 1961. This register thus provides information on censoring (death and emigration) of study subjects, and can also be used to identify a general population comparison cohort.

#### 9.5. Study Size

All eligible patients in the Swedish registers will be included, with no upper limit on the sample size. The feasibility of more refined comparative analyses to evaluate safety concerns that adequately adjust for patient channeling and confounders will be assessed at an interim time point and after 7 years will be based on statistical power. Since the comparator groups will be a magnitude larger than the tofacitinib treated group, statistical power will be limited by the uptake of tofacitinib, which is difficult to estimate a priori. While the primary objective of the protocols is active surveillance, conducting quantitative, confounding controlled comparisons will depend on having a sufficient sample.

Table 2 and Table 3 below describe the power to detect a 2-fold difference in event rates between tofacitinib-initiators and bDMARD-initiators assuming the following:

- $\alpha=0.05$ ;
- 3 different bDMARD-treated patient population sizes (reflecting roughly range of EU registers):  $n=11100$ ,  $n=5050$ ,  $n=1650$ ;
- 4 different tofacitinib-treated patient population sizes:  $n=100$ ,  $n=250$ ,  $n=500$ ,  $n=1000$ ;
- Estimated rates on bDMARD of 30/1000 person years (PY) (eg, serious infection), 10/1000 PY (eg, malignancy excluding NMSC), and 6/1000 PY (eg, major adverse cardiovascular event (MACE)) based on previous analysis with registers (Pfizer, internal data);
- 7-year study period;
- Constant rate of accrual;
- 5% annual loss to follow up among tofacitinib-treated patients.

Additionally, Table 2 assumes a 0% annual rate of switching off tofacitinib, as would be true for a drug with very high persistence or for an analysis following the once exposed always at risk paradigm. Table 3 assumes a 30% annual rate of switching from tofacitinib to a bDMARD over the study period, as previously demonstrated in the EU for bDMARDs in Italy.

For an event with a rate of 30/1000 PY, such as serious infections, 250 patients would allow sufficient power to detect a 2-fold difference in rates between tofacitinib and bDMARD-exposed patients assuming very high persistence (Table 2), while 500 tofacitinib exposed patients would be nearly sufficient if 30% of tofacitinib treated patients switched off of tofacitinib annually.

For an event with a rate of 10 cases per 1000 PY, such as malignancy excluding NMSC, a sample of 500 patients approaches 80% power in a medium (n=5050) to large (n=11,100) register when patient time continues to accrue after drug discontinuation (Table 2). It will be a challenge to achieve sufficient power in a register with fewer bDMARD exposed patients. Nonetheless, replication of a similar trend in an underpowered sample could be locally informative.

For an endpoint with an event rate of 6/1000 PY, such as MACE, even assuming high persistence (Table 2) a sample size of 1000 tofacitinib patients within a registry with more than 5000 bDMARD patients would be required to make well-powered comparison. In a scenario with a 30% annual rate of switching off of tofacitinib, 1000 tofacitinib treated patients and 11 100 bDMARD patients would only provide 40% power to detect a 2-fold difference (Table 3).

Prior to conducting any analyses, a feasibility assessment will be conducted to determine the approximate power of planned comparative analyses.

**Table 2. The Power To Detect A Two Fold Difference In Risk Among Tofacitinib Exposed Patients Compared With bDMARD Treated Register Patients Given Different Assumed Sample Sizes, alpha = 0.05, 5 Year Study With Uniform Accrual, 5% Loss To Follow Up Per Year In Tofacitinib Arm**

Number of tofacitinib exposed patients	~11100 bDMARD-treated patients	~5050 bDMARD-treated patients	~1650 bDMARD-treated patients
bDMARD rate ~ 30/1000 PY (eg, serious infections)			
100	0.46	0.45	0.44
250	0.92	0.91	0.88
500	1.00	1.00	0.9
1000	1.00	1.00	1.00
bDMARD rate ~10/1000 PY (eg, malignancy)			
100	0.11	0.12	0.12
250	0.38	0.38	0.36
500	0.75	0.73	0.66
1000	0.98	0.96	0.89
bDMARD rate ~ 6/1000 PY (eg, MACE)			
100	0.06	0.06	0.06
250	0.20	0.20	0.20
500	0.47	0.46	0.41
1000	0.83	0.79	0.68

090177e199570500\Approved\Approved On: 13-Feb-2022 20:25 (GMT)

**Table 3. The Power To Detect A Two Fold Difference In Risk Among Tofacitinib Exposed Patients Compared With bDMARD Treated Register Patients Given Different Assumed Sample Sizes, alpha = 0.05, 5 year Study With Uniform Accrual, 5% Loss To Follow Up Per Year In Tofacitinib Arm, 30% Switch From Tofacitinib to bDMARD Per Year**

Number of tofacitinib exposed patients	~11100 bDMARD-treated patients	~5050 bDMARD-treated patients	~1650 bDMARD-treated patients
bDMARD rate ~ 30/1000 PY (eg, serious infections)			
100	0.18	0.18	0.18
250	0.50	0.49	0.46
500	0.84	0.82	0.75
1000	0.99	0.98	0.93
bDMARD rate ~10/1000 PY (eg, malignancy)			
100	0.06	0.06	0.06
250	0.16	0.16	0.15
500	0.33	0.32	0.30
1000	0.64	0.60	0.50
bDMARD rate ~ 6/1000 PY (eg, MACE)			
100	0.04	0.04	0.04
250	0.09	0.09	0.09
500	0.19	0.19	0.18
1000	0.40	0.38	0.32

Based on the first 9 months of enrolment of tofacitinib-exposed patients in ARTIS, 344 patients are projected to be enrolled in the first 24 months, allowing at least 5 years follow up by the end of the planned study period, assuming the initial rate remains constant over the period.

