**Data Analysis:** The initial analyses will consist of descriptive comparisons of baseline status and crude event rates between the different cohorts. The final analysis of endpoints will provide the rates of events overall and in subgroups defined by baseline characteristics. Pending feasibility, rates of malignancy (overall, excluding NMSC), lymphoma (overall and by subtype), lung cancer, serious infection, CV events, VTE, and other event rates will be compared between tofacitinib-treated RA patients and the comparator cohorts using methods that adjust for sex, age, year of treatment start, treatment history, disease severity, comorbidities, and other potential confounders. For lymphoma, incidence rates will be stratified by lymphoma subtypes; not limited to but including non-Hodgkin lymphoma (NHL), Hodgkin lymphoma, chronic lymphatic leukemia. Similarly, CV (e.g. myocardial infarction (MI), MACE, serious congestive heart failure) and VTE (DVT and PE) event rates will be stratified by type of event. Further, for the outcomes of MI and MACE, incidence rates of the safety events of interest will be stratified by patients with  $\geq 1$  CV risk factors versus no CV risk factors. Similarly, for the outcome of VTE, incidence rates of the safety events of interest will be stratified by patients with  $\geq 1$  VTE risk factors versus no VTE risk factors.

**Milestones:** Interim reports will be provided at 2, 4, 6 years after the start of data collection. A final report, including linked data, will include 7 years of data after start of data collection.

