## 6. MILESTONES

Milestone	Planned date
-----------	--------------

Registration in the EU PAS register	01 September 2019
Start of data collection	15 September 2019
Interim report	14 March 2021
Interim report	14 March 2023
Interim report	14 March 2025
End of data collection	14 September 2025
Final Study Report	14 August 2026

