Using this primary analytic approach, if neither tofacitinib nor bDMARDs cause an increased risk of malignancy both exposure cohort rates will reflect the background rates of malignancy from the time of index to the end of the study period and the comparative effect measure will indicate no difference in rates. If tofacitinib does cause an increased rate of malignancy, which is the effect we are most interested in detecting, a relatively higher rate will be observed in the tofacitinib exposed cohort. The once exposed always at risk approach is therefore able to detect an increased rate given the non-random switching expected to occur given use of bDMARDs prior to tofacitinib and is consistent with previous studies evaluating the risk of individual biologics. Additional analyses will be conducted to evaluate potential confounders and the impact of different latency assumptions as will be described in the statistical analysis plan (SAP). Sensitivity analyses will be conducted that restrict the bDMARD comparator cohort to patients who were never exposed to tofacitinib or other non-biologic advanced therapies and compare the characteristics of those bDMARD patients ever and never exposed to tofacitinib.

Secondary analyses that censor follow up time after a switch to a different treatment class will also be performed. Among patients indexed to a bDMARD cohort, follow up will begin at index and continue until the first of an event, switch to tofacitinib or other non-biologic advanced systemic therapy, loss to follow up, death, or study end date. Similarly, for tofacitinib, follow up will begin at index and continue until the first of an event, switch to a non-JAK inhibitor-based advanced systemic therapy, loss to follow up, death or study end date. While this approach eliminates the problem of double counting, it may not allow sufficient follow up time to allow for latent effects or detection and decreases the number of events included reducing the statistical power to detect a higher risk of malignancy in tofacitinib treated patients. However, under an assumption of no latency or a very short latent period as in an aggressive tumor promoter, this approach would detect an increased risk of disease on tofacitinib relative to the risk due to bDMARDs.

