### **9.7.2. Final Safety Report**

The feasibility of conducting a final comparative study will be evaluated at an interim time point and at 7-years of follow up based on statistical power and suitable overlap in patient populations in the exposure groups. The feasibility assessment, like the final report, will be conducted using safety events of interest identified through linkages with the patient, cancer and death registers, as appropriate. ARTIS will apply an ICD-code based algorithm to identify serious infections, GI perforations, herpes zoster, and CV events (MACE), in the Swedish patient register. Appendix 4 describes the algorithms used to identify these endpoints in ARTIS and relevant validation references, along with definitions used by other EU registers. The specific algorithms for defining those endpoints have not been validated, though the Swedish patient register has been validated several times (Ludvigsson 2011). The overall positive predictive value (PPV) of the inpatient diagnoses generally ranged from 85% to 95%. A regional validation study of hospitalized acute MI and stroke (components of the MACE endpoint) found positive predictive values of 96% and 94% respectively, in the period 1977 to 1987 (Lindblad, 1993). An ICD-9 code based algorithm applied to inpatient diagnoses of GI perforations in the US demonstrated high PPV (89.1-100) (Curtis, 2011). While the ICD algorithms used by ARTIS to define the endpoints of interest may not be validated, their use can be justified given the importance to contextualize the study results with historical findings. ARTIS has previously conducted and published studies of serious infections (Askling, 2007), PML (Arkema, 2012), and MACE (Michaud, 2016) events in RA patients.

The Swedish national register for contagious diseases, will serve as source of information on TB and other possibly serious contagious diseases for which there is a mandatory registration in Sweden. These reports will be based on a standardized analytical scheme, with some but limited flexibility to add additional endpoints and stratification, and will contain populated tables in line with the shells in Appendix 2. Whether these reports include formal comparisons of patients exposed to tofacitinib and bDMARDs will be determined a priori based on adequate power.

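### Power Tables 2 and 3 do not follow from the assumptions in Section 9.5: they fit a lower, not a doubled, tofacitinib risk, and 5 years rather than the listed 7

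*Protocol*

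**What the plan says.** Section 9.5 introduces both tables as ones that "describe the power to detect a 2-fold difference in event rates between tofacitinib-initiators and bDMARD-initiators assuming the following", and then lists the inputs. The comparator rates are attached to the bDMARD arm: "Estimated rates on bDMARD of 30/1000 person years (PY) (eg, serious infection), 10/1000 PY (eg, malignancy excluding NMSC), and 6/1000 PY". The list also gives alpha 0.05, a 7-year study period, a constant accrual rate, and 5% annual loss among tofacitinib patients. Table 2 assumes no switching. Table 3 assumes that 30% per year switch from tofacitinib to a bDMARD.

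The Table 2 caption reads "alpha = 0.05, 5 Year Study With Uniform Accrual, 5% Loss To Follow Up Per Year In Tofacitinib Arm". The Table 3 caption also says 5 years.

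The two-fold difference carries no direction in Section 9.5. Section 9.3.2 supplies one for malignancy: "If tofacitinib does cause an increased rate of malignancy, which is the effect we are most interested in detecting".

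The text draws planning conclusions from individual cells, for example that with 30% switching "1000 tofacitinib treated patients and 11 100 bDMARD patients would only provide 40% power to detect a 2-fold difference" in MACE. Section 9.7.2 makes the comparative work depend on power: "Whether these reports include formal comparisons of patients exposed to tofacitinib and bDMARDs will be determined a priori based on adequate power".

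**The concern.** Three signs of trouble are visible before any modelling.

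- The assumption list (7 years) and both captions (5 years) cannot describe the same calculation.
- In Table 2 at 30/1000, the cell for 500 against 1650 is 0.9, where the rows above and below read 0.88 and 1.00. The two neighbouring cells in its row are both 1.00.
- Table 3 prints 0.04 for MACE with 100 tofacitinib patients, which is below alpha. In the usual log-rank approximation that happens when the small arm has the lower risk, not the higher.

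If the arms were swapped, the tables answer a different question from the one a safety study asks. The distortion would be largest at small tofacitinib numbers. Section 9.5 projects 344 tofacitinib patients in the first 24 months, which lies between the 250 and 500 rows.

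**Working it through.** **Inputs.** All are from Section 9.5: rate R = 30, 10 or 6 per 1000 person-years; two-fold ratio; alpha 0.05, taken as two-sided (not stated, but two-sided fits); bDMARD n = 11,100, 5050, 1650; tofacitinib n = 100, 250, 500, 1000; uniform accrual over the whole period; 5% annual loss; 0% or 30% annual switching. Event times are taken as exponential, and an annual proportion p becomes a rate −ln(1−p).

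**Formula.** Step through follow-up time. At each step let d_T and d_B be the expected events on tofacitinib and bDMARD, and p the tofacitinib share of those at risk. Then

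- E = Σ[d_T − (d_T + d_B)p]
- V0 = Σ(d_T + d_B)p(1−p)
- V1 = Σ[d_T(1−p)² + d_B p²]
- power = Φ((|E| − 1.96√V0)/√V1)

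**Reproducing the printed figures.** Put tofacitinib at R and bDMARD at 2R, for 5 years, with loss and switching in the bDMARD arm.

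- Table 2, malignancy, 500 vs 11,100: E = −11.71, V0 = 22.86, V1 = 12.27. (11.71 − 1.96×4.78)/3.50 = 0.67, so power is 0.75. Printed 0.75.
- Table 3, MACE, 1000 vs 11,100: E = −8.12, V0 = 20.92, V1 = 14.23. (8.12 − 1.96×4.57)/3.77 = −0.22, so power is 0.41. Printed 0.40.
- Table 3, MACE, 100 vs 11,100: E = −0.88, V0 = 2.34, V1 = 1.48, so power is 0.04. Printed 0.04.

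Across all cells this model matches 35 of 36 in Table 2 and 36 of 36 in Table 3 to within 0.02. The one miss is the 0.9 cell, which recomputes to 0.99. The same swapped model at 7 years misses most of Table 2 (about 30 of 36 cells).

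**Using the stated inputs, for a doubled risk.** Put tofacitinib at 2R and bDMARD at R, with loss and switching on tofacitinib.

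- Malignancy, 500 vs 11,100, 5 years: E = 10.70, V0 = 11.12, V1 = 20.98. (10.70 − 1.96×3.33)/4.58 = 0.91, so power is 0.82.
- Same cell, 7 years: E = 14.36, V0 = 14.90, V1 = 28.16. (14.36 − 1.96×3.86)/5.31 = 1.28, so power is 0.90.

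Cells missing by more than 0.02: Table 2, 25 of 36 (5 years) and 30 of 36 (7 years); Table 3, 33 of 36 at both. Root-mean-square error is about 0.15 and 0.22 for Table 2, and 0.13 for Table 3.

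**What the cells should say**, with 11,100 bDMARD patients. The exact column is a conditional binomial test on Poisson counts (20,000 draws).

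| Cell | Printed | Log-rank 5 / 7 y | Exact 5 / 7 y |
|---|---|---|---|
| Table 2, malignancy, 250 | 0.38 | 0.60 / 0.70 | 0.47 / 0.59 |
| Table 2, malignancy, 500 | 0.75 | 0.82 / 0.90 | 0.76 / 0.87 |
| Table 2, malignancy, 1000 | 0.98 | 0.97 / 0.99 | 0.96 / 0.99 |
| Table 2, MACE, 500 | 0.47 | 0.65 / 0.76 | 0.55 / 0.67 |
| Table 2, MACE, 1000 | 0.83 | 0.86 / 0.94 | 0.82 / 0.92 |
| Table 3, malignancy, 500 | 0.33 | 0.51 / 0.51 | not run |
| Table 3, MACE, 1000 | 0.40 | 0.55 / 0.56 | not run |

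The log-rank values move by up to about 0.01 with the form of V1.

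**Does reading the difference as a halving rescue the tables?** Put tofacitinib at R/2 and bDMARD at R, keeping uniform accrual and loss and switching on tofacitinib. Root-mean-square error is then 0.25 (5 years) and 0.16 (7 years) for Table 2, and 0.22 and 0.21 for Table 3. Table 2 alone does fit R/2 against R (error 0.005), but only if every patient has 5 full years and there is no accrual period or loss. Tofacitinib is still the lower arm there.

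**The case against.** The strongest reply is that nothing is decided by these tables. The study is descriptive, has no prespecified hypotheses and takes every eligible patient. Section 9.5 also promises a separate feasibility assessment of power before any analysis. That stands. A reader might infer that the tables are themselves the feasibility rule, or that a MACE or malignancy comparison will be wrongly abandoned because of them; the protocol supports neither.

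Second, the size of the error depends on the test and the duration. That also stands. With the exact test at 5 years, malignancy at 500 to 1000 and MACE at 1000 are about level with print, so the main Table 2 conclusions (500 close to 80% for malignancy, about 1000 needed for MACE) survive there. It would be wrong to say that every cell understates power.

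Third, the swapped-arm diagnosis is an inference about a program nobody has seen, and the fit is not unique. True, but every variant found that fits Table 2 has tofacitinib as the lower-risk arm and 5 years. The failure of the stated inputs does not depend on the diagnosis.

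Two further readings should be resisted. Treating the 30% switching as censoring raises Table 3 power further, but Section 9.5 specifies switching to a bDMARD, so the like-for-like values are those in the table. And the abstract's "A final report, including linked data, will include 7 years of data after start of data collection" set against an end of data collection of "14 September 2025" (6.0 years after 15 September 2019) might suggest that only six years of follow-up exist, less the register lag. Section 9.2.1 has the product fully available from April 2017, and the Annex 2 footnotes define start and end of data collection by data extraction and dataset availability. So the milestone interval is not the follow-up time; at most that wording is loose.

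**Conclusion.** The point holds. The figures in Tables 2 and 3 do not follow from the assumptions listed above them, and they are not the power to detect a doubled risk on tofacitinib. They fit 5 years with tofacitinib as the lower-risk arm; the list says 7 years and the direction of interest is the opposite. For a doubled risk, most printed values are too low by the log-rank calculation. The gap is largest at small numbers and low rates: 0.22 (5 years) to 0.32 (7 years) for malignancy at n = 250, and about 0.15 for MACE at n = 1000 with switching. A few cells near saturation are level or 1 to 2 points too high at 5 years.

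This rests on exponential event times, a two-sided test, and loss and switching placed on tofacitinib as stated. The identified cause is the best fit among the variants tried, not a proven history.

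**What to change.** Re-run both tables with the direction written out (tofacitinib at twice the stated bDMARD rate), loss and switching in the tofacitinib arm as listed, the test and its sidedness named, and one study duration used in both the assumption list and the captions. Correct the 0.9 cell. Revise the paragraphs in Section 9.5 that quote the tables, including the 40% figure for MACE. Carry the corrected assumptions into the feasibility assessment that Section 9.5 promises. While editing, clarify what the abstract's 7 years are counted from, so that it reads consistently with the milestones.

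The cost is one re-run of a power program and a text edit. No design change, patients or data are involved.
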